## **1 Background**

### ***1.1 Obstructive Sleep Apnea (OSA) in a clinical context***

Sleep apnoea is a common disorder in the Norwegian, adult population. A Norwegian study has estimated the prevalence of OSA defined by an Apnoea Hypopnea Index (AHI) of  $\geq 15$  to be 8 % among adults aged 30-65 years . If untreated, OSA is associated with increased risk of cognitive impairment, cardiovascular morbidity, mortality and daytime sleepiness .

Treatment with positive airway pressure (PAP) has been shown to reduce cardiovascular risk, to relieve symptoms and to be cost-effective in patients with moderate to severe OSA . However, approximately 25% do not adhere to treatment and patients who adhere uses the machine less than prescribed . Complementary, less efficient treatment modalities for OSA are: Lifestyle change , positional therapy , mandibular advancement devices (MAD)  and surgery .

Treatment with PAP is cumbersome. Accordingly, in mild to moderate OSA novel treatment options are warranted . Orofacial myofunctional therapy (OMT) has in a recent Cochrane report been shown to be effective in mild to moderate OSA . However, more randomized controlled trials (RCTs) with blinded assessment of end points and intention to treat design are needed. Auto-monitoring through participatory health technology is a promising method for the increase of treatment adherence.

## **Aims and hypotheses**

## **2.1 Overall research aims**

The overall aim of this study is to estimate the effect of OMT plus auto-monitoring (OMTa) compared to auto-monitoring alone. Moreover, we aim to identify anatomical and behavioural predictors of OMTa adherence.

## **3.0 Material and methods**

**The study is a single blinded RCT with blinded outcome evaluation and intention to treat analysis.** The participants will know by default if they are allocated to the OMTa or waiting list with auto-monitoring during the 90-day intervention period. Blinded baseline- and outcome assessments will be performed by one doctor ([name]) in Norway and one doctor ([name]) in Estonia.

### **3.1 Material**

Patients referred to the Otorhinolaryngology department at Akershus University Hospital (Ahus), Norway and the Fertilitas Private Hospital (FPH) in Tallinn, Estonia. Eligible patients with a suspected or confirmed diagnosis of OSA will be asked to participate in this RCT. An informed consent form will be given or sent to the participant together with information to log in to the mobile application (app). The mobile app contains an electronic sleep diary based on the consensus sleep diary (appendix 1).

#### Inclusion criteria:

- Patients referred to Ahus or the Fertilitas clinic
- A diagnosis of obstructive sleep apnea according to the current International Classification of Sleep Disorders (ICSD) version 3 criteria {Berry, 2020, The AASM Manual for the Scoring of Sleep and Associated Events: Rules, Terminology and Technical Specifications, Version 2.6., 2014, International classification of sleep disorders, 3rd ed.}, with a respiratory event index (REI) <30.
- Not previously or currently treated with PAP or MAD
- Signed informed, written consent.
- Owning a mobile phone with software compatible for the study application

- Age  $\geq$ 18 year.
- Body mass index  $<$ 30
- Ability to breathe through the nose
- Ability to read and willingness to follow the protocol as described in the written consent form
- Teeth 5-to 5 should be present or fixed by prosthesis or implants.
- No botulinum toxin in facial muscles last three months

Exclusion criteria:

- Failure to fill in at least 70% of days in the electronic sleep diary provided in the mobile app for two weeks.
- Medical or psychiatric conditions which may interfere with the study protocol in the opinion of the investigator. Examples are acute psychosis, drug abuse and dementia. This will be noted in the study inclusion-exclusion document for each approached candidate for the study. The information will then be discussed in an exclusion committee consisting of dr. [name], [name], [name] and [name].
- Tongue-tie as described below. Participants with mouth opening of  $<$ 50% with the tip of the tongue at the incisive papilla compared to total mouth opening will be excluded.

Inclusion criteria will be assessed by the otorhinolaryngologist establishing an OSA diagnosis or the project co-ordinators.

### ***3.2 Methods***

#### **Prior to the baseline consultation**

All participants will receive a standardized information sheet with login information to the electronic sleep diary. Support on using the application prior to the baseline evaluation will be available by the study co-ordinators by telephone. Evaluation of exclusion criteria will be assessed prior to- or at the baseline study visit. Excluded patients will be referred back to clinical care. Signed informed consent will be obtained and archived on paper.

### **Baseline evaluation**

Eligible candidates completing auto-monitoring less than 70% of the days prior to baseline assessment will be excluded (see exclusion criteria above). Questions related to the “Sleep Well” application will be answered. [name] and [name] respectively will also ensure that at least 40 of 100 participants are female. After final inclusion, [name] and [name] respectively will schedule the sleep registration and an outcome evaluation session 90 days later. All data collected during the baseline evaluation will be collected in the “Redcap” case report form (CRF).

Further, clinical evaluation will consist of height, weight, standardized blood pressure and a breath holding test. Digital oral scanning will be obtained at both sites. Thereafter, the quantitative scores (OMES) for assessing the myofunctional therapy will be performed and video filmed with one front camera and one camera with a 45-degree angle on the face. The purpose of the video filming is inter rater reliability analyses. All participants will be placed in a chair without arm- or backrest. Body posture on the chair will not be corrected. The baseline assessment will last approximately 90 minutes.

#### Baseline assessment includes:

- **OMES-protocol** Appearance/Posture: face (symmetry), cheeks, mandible, lips, tongue and hard palate. Mobility: Subjects will be asked to perform 4-6 movements with each component of lips, tongue, cheeks and mandible.
- Functions: breathing mode, deglutition and mastication.
- The maximum possible score for functions will be 29 (breathing=3, deglutition=16, mastication= 10).
- Tongue movement described in the OMES protocol.
- **Additional tongue assessment:** Evaluation of tongue tie using the quick-tongue tie assessment tool for measurements of Maximal interincisal mouth opening (MIO, mm) and interincisal mouth opening with tongue tip to maxillary incisive papillae at a roof of the mouth (MOTTIP) .

- **Oral scanning:** 3D dental scanning will be performed at both sites. Pseudonomized electronic files will be analyzed with the “Dolphin®” software ([Dolphin Ceph Tracing | Dolphin Imaging Software](#)) in Estonia.
- **Height measurement:** The participant will be asked to stand barefoot in an upright position with their heels, buttocks, and upper back up to the wall and their head facing directly ahead. Feet together and arms by the sides. The distance from the floor to the highest point of the head will be measured by the nearest 0.1cm. The total height (cm) will be recorded.
- **Weight measurement:** The participant will be asked to step barefoot on a stand-alone unit with a digital scale. The Body mass will be measured with an accuracy of 100g. Participants will be asked to remove shoes and socks as well as heavy jumpers/jackets/jeans. The total weight (kg) will be recorded.
- **Body Mass Index (BMI): BMI will be calculated by** the formula of body mass (kg) divided by height squared (m^2) (kg/m^2)
- **Waist Hip Ratio:** Waist and hip circumference will be assessed in manual measurements with flexible but non-stretchable tape with an accuracy of 1mm. The waist circumference will be measured at the midpoint between the last rib and the Iliac Crest. The hip circumference will be measured at the level of the largest lateral extension of the hip. Both measures will be assessed in the horizontal plane. The waist and hip circumference will be recorded and the Waist Hip ratio will be calculated using the formula of waist circumference divided by hip circumference.
- **Neck Circumference:** Neck circumference will be measured with a flexible but non-stretchable tape measure with an accuracy of 1mm. The neck circumference will be measured in the midway of the neck, between the mid-cervical spine and mid-anterior neck. The subject will be asked seat relaxed with the arms hanging by their side and to maintain the head in the Frankfort Horizontal plane. For men, the measure will be taken immediately superior to the Thyroid cartilage (Adam’s apple). The total neck circumference will be recorded (cm).

**Hand grip strength** assessed by hand dynamometry of the dominant hand will be evaluated with a Jamar hand dynamometer ([Jamar Hydraulic Hand Dynamometer \(5030J1\) | JLW Instruments \(jlwforce.com\)](#)). The grip strength

will be measured in a face-to-face assessment with the participant sitting on a chair with a back support and fixed arm rests, feet on the ground. Their wrist should be just over the end of the arm rest, with the thumb facing upwards. The examiner should encourage the participant to squeeze as long and as tightly as possible until the needle stops rising. The measurement from the dial should be recorded to the nearest 1kg. If the participants arm rises above the chair the measurement should be disregarded. Three measurements will be recorded for each hand, while alternating sides ([Procedure for measuring gripstrength using the JAMAR dynamometer \(uhs.nhs.uk\)](#)).

### ***Chewing test***

A standardized chewing efficiency test is performed with the CHEW Box Digital Reporting services (DRS CHEW box) from Orehab Minds (<https://www.orehab-minds.com/>). The patient is instructed to perform 9 chewing sequences with standardized gelatin test units of soft, medium and hard consistency. Each sequence consists of chewing for 30 seconds with 30 seconds intermission, first only on the right side, next only on the left side and last on both sides, alternating every 5 seconds. Participants will be instructed to “divide as many pieces as you can”. The chewed-up pieces of the test unit are spitted out in a sieve, rinsed and distributed on a plate which is placed inside the DRS CHEW box. The box takes a picture with standardized lighting, angle and camera distance. The 9 pictures from each chewing test are uploaded to a central database where they are analyzed. No identifying patient data is stored in this system. This results in a report where number of particles, average size, and distribution ratio of particle size is calculated. A comparison of chewing efficiency differences between sides and consistencies is presented both graphically and numerical, and is compared to a normal distribution for healthy adults.

*The Iowa oral performance instrument (IOPI), <https://iopimedical.com/>*, is used to measure the pressure of anatomical structures in the oral cavity. The calibration of the device was tested against another device in January 2022. Tongue strength will be assessed at baseline and after 12 weeks of OMTa. The subject will be instructed to place and press a disposable, standard-sized bulb as hard as possible with the tongue against the roof of the mouth for 2–3 seconds. The maximum pressure is demonstrated as tongue strength in kilopascals (kPa). After obtaining the measured value, the measurement will be repeated two additional times and the highest value will be scored. In addition, the subject will be instructed to maintain 50% of the highest pressure as long as possible. The maintained duration of time will be recorded as tongue endurance.

*Lateral cephalography* is applied to assess the oral maxillofacial anatomy. Participants are asked to relax their face and mouth, keep the teeth in centric occlusion, swallow once and hold the tongue in the position. The cephalograms are taken at 73 kVp and 15 mA, in natural head position with the patient's sagittal plane parallel to the X-ray film and the Frankfort plane parallel to the floor. [name] will trace all the required landmarks on the cephalograms. This preliminary cephalometric study mainly focuses on anatomical variables related to OSA. Four variables related to tongue morphology will be registered. In addition, hyoid position will be represented by the distance between the hyoid bone and the mandibular plane.

*Patient reported outcomes collected during baseline evaluation:*

The BEAMER questionnaire is being developed in a current, large study funded by the innovative medicines initiative. The core version consists of one visual analogue scale assessing general health, three questions assessing control and three questions assessing acceptancy.

The Epworth sleepiness scale (ESS) is a 8-item measure of daytime sleepiness. The questionnaire has been validated in a Norwegian population.

The physical health questionnaire (PHQ) is a 9-item measure of depression.

The questionnaire has been validated in a Norwegian population .

The General anxiety Disorder (GAD) questionnaire is a 7-item measure of anxiety

. The questionnaire has been validated in a Norwegian population .

The DS-14 questionnaire is assessing type D personality. The questionnaire has been validated in the Akershus Sleep Apnea Project .

#### *Wearable technology*

All participants will be asked to wear a Withings Scanwatch,

<https://www.withings.com/be/en/scanwatch>, programmed in research mode.

The research mode setting implies that the watch operates as a sensor. The patients can monitor their own sleep quality data inside the Withing's mobile application. Participants will be instructed to open the Withings application daily.

#### **Randomization**

At the end of the baseline consultation participants will be randomized to either OMTa or only auto-monitoring. Block-randomization with 10 lots per block, per study site, and a 50/50 allocation ratio will be used for waiting list and intervention and separated by sex in order to monitor the 40/60 gender balance. The lots will be made as a code on paper and concealed in opaque envelopes at each study centre. Each participant will also receive a unique e-mail address and a password in the same envelope. The randomization envelopes will be made and mixed by dr. [name]. Envelopes will be sent to dr [name] in Estonia. Both researchers will be blinded for the content in the envelopes.

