### **Description of the intervention**

Participants opening a code unlocking the OMTa treatment module of the application will be given a direct communication link to the PhD students, [name] (Norway) and [name] (Estonia) and two research co-ordinators. [name] and [name] has obtained an Academy of Orofacial Myofunctional Therapy (AOMT) certification diploma. One physical start up session will be scheduled at Ahus and at North Estonia Medical Center. This 60 minute session will be used to instruct participants in OMT exercises and use of the app. All participants will receive a disposable toothbrush and standardized balloons. After that, biweekly video sessions (time 20-30 min) will be scheduled. The exact same amount of sessions and equipment will be offered to the waiting list group after the outcome evaluation. The following exercises are pre-recorded and presented in the treatment module:

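### A single disclosed block size of 10 per site and sex, in envelopes held at the centres, lets anyone who knows the earlier allocations foresee about one in six with certainty; this is an avoidable weakness, not evidence of bias.

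*Combined protocol and SAP*

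**What the plan says.** The Randomization section (under 3.2 Methods) sets one block size and a 1:1 ratio: "Block-randomization with 10 lots per block, per study site, and a 50/50 allocation ratio". The lots are also "separated by sex in order to monitor the 40/60 gender balance", which gives 2 sites × 2 sexes = 4 strata. On custody it says: "The lots will be made as a code on paper and concealed in opaque envelopes at each study centre". One researcher makes and mixes the envelopes and sends a supply to a colleague in Estonia. The stated safeguard is that "Both researchers will be blinded for the content in the envelopes". The envelope is opened at the end of the baseline visit.

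The plan does not mention varying block sizes, a computer-generated list, sequential numbering, an envelope log or central allocation.

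Four other places bear on the point:

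- **Section 3.0** calls the trial single blinded, with blinded baseline and outcome assessment. It accepts that participants know their arm.
- **Description of the intervention**: OMTa participants "will be given a direct communication link to the PhD students" and to two research co-ordinators. They also have a start-up session and regular video sessions.
- **Inclusion and exclusion criteria (3.1)**: "Inclusion criteria will be assessed by the otorhinolaryngologist establishing an OSA diagnosis or the project co-ordinators". Exclusion for an interfering medical or psychiatric condition rests on the investigator's opinion, but it is recorded for each candidate and discussed in an exclusion committee.
- **Prior to the baseline consultation (3.2)**: exclusion may be decided before the baseline visit or at it, so before the envelope is opened.

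**The concern.** Opaque envelopes hide the next code. They do not hide what can be inferred from codes already opened. When the block size is fixed and printed in the protocol, each block must end at five and five, so known past allocations progressively determine the rest.

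Some staff do learn past allocations. Those who deliver or support OMTa know who is in it, and other enrolled participants must be on the waiting list. The declared blinding covers the two researchers who prepare and receive the envelopes. It does not cover the PhD students or the co-ordinators. It can also hold only for the order of the codes, because whoever makes the envelopes knows the five-and-five structure.

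If someone with this knowledge could influence whether or when a candidate enters, the arms could differ before treatment starts. Intention-to-treat analysis and blinded scoring act after that step and do not correct it. The comparisons in section 6.1 (a Kruskal-Wallis test at each time point) include no baseline adjustment.

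**Working it through.** The plan gives no figure for predictability, so there is none to reproduce. Its sample size is not in dispute here.

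**Inputs.** Block size 2b = 10, so b = 5 per arm (Randomization). Strata: site × sex (Randomization). Total 100 participants (6.2), at least 40 of them women (Baseline evaluation). The observer is assumed to know the block size and every earlier allocation in the stratum.

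**Step 1: allocations certain in advance, fixed block of 10.** Once one arm has used its five places, the rest of the block is known.

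- Expected number certain = 2b/(b+1) = 10/6 = 1.67 per block, or 16.7%.
- Enumerating all C(10,5) = 252 orderings gives the same mean. The last allocation is always certain. At least the last two are certain in 44.4% of blocks, the last three in 16.7% and the last four in 4.8%.

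**Step 2: allocations guessed correctly.** The strategy is to guess the arm that is behind.

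- Expected correct = b + 2^(2b−1)/C(2b,b) − 1/2 = 5 + 512/252 − 0.5 = 6.53 of 10, or 65.3%, against 50% by chance.

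**Step 3: scale to the trial.** Assume 20 women and 30 men per site, so that 100 participants fill 10 whole blocks. Then at least 10 allocations, and on average 10 × 1.67 = 16.7, are certain in advance. Incomplete final blocks lower this.

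**Step 4: would shorter fixed blocks help?** No. The same formulas give:

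| Fixed block | Certain | Guessed correctly |
|---|---|---|
| 4 | 33.3% | 70.8% |
| 6 | 25.0% | 68.3% |
| 8 | 20.0% | 66.6% |
| 10 | 16.7% | 65.3% |

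**Step 5: varying sizes.** Simulation, with strata of 20 and 30 assumed:

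- Sizes drawn at random from 8, 10 and 12: an observer who knows the possible sizes but not their order has about 1.6% certain allocations. Guessing the arm that is behind is right about 64% of the time.
- Sizes drawn from 4, 6 and 8: guessing is right 67 to 68% of the time, which is worse than a fixed 10.

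Varying the size around 10 thus removes nearly all the certainty and almost none of the guessability. Guessing is limited only by keeping the running allocations from those who decide on entry.

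**The case against.** The strongest reply is that the documents do not show anyone in a position to use this knowledge.

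- Most eligibility criteria are objective: REI and BMI limits, age, no previous PAP or MAD, dentition, mouth-opening ratio and diary completion. The opinion-based exclusion is logged and goes to a committee.
- Candidates keep a two-week sleep diary before baseline. Someone judging inclusion at diagnosis can hardly know which envelope will be next weeks later. Steering would have to happen close to or at the visit, where the assessing doctors are declared blinded.
- Inclusion is judged by project co-ordinators, while OMTa participants are linked to research co-ordinators. Names are removed from the public text, so overlap can be neither shown nor excluded. The envelope preparer may already be independent of enrolment, assessment and therapy.
- Varying the block size changes best-guess accuracy by only about one percentage point.

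All of this stands, and it limits the point to a vulnerability. It does not remove it: no sentence bars people who know the allocations from judging or timing entry, and the certainty at the end of each block is avoidable.

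A reader might infer more than the text supports. The trial is not open throughout, but only to participants and treating staff. Envelope storage is not described, so it cannot be said that staff could count the envelopes left in a block. It would also be too absolute to say that no analysis could help, since imbalance in measured baseline variables can be examined and adjusted for; imbalance in unmeasured ones cannot.

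**Conclusion.** The point holds as a minor, cheaply avoidable design weakness. With one disclosed block size of 10 per site and sex, an observer with full knowledge of a stratum's history can foresee 16.7% of allocations with certainty and guess 65.3% correctly. Both figures assume complete knowledge of earlier allocations, and the first also assumes completed blocks; with less knowledge they fall. Ten is already a fairly long block, and shorter fixed blocks would be worse.

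It does not follow that selection bias has occurred or is likely. The documents do not show that allocation-aware staff also judge eligibility, and no effect on the AHI comparison can be calculated from them.

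**What to change.** In the Randomization section, replace the fixed block of 10 with a computer-generated list of randomly varying block sizes around 10 (for example 8, 10 and 12) within site and sex. Keep the sizes out of any document the sites see, and use sequentially numbered opaque envelopes. Add a sentence that whoever confirms eligibility has no access to the running allocations in that stratum. State the role of the person who prepares the list and envelopes, who should have no part in enrolment, assessment or therapy. If these roles are already separate, saying so is enough.

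The varying sizes address certainty; the restriction on access addresses guessing. Both are needed.

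The cost is a new list and a few lines of protocol text. The downside is a slightly larger possible imbalance if recruitment stops within a block: at most 12/2 = 6 in a stratum, instead of 10/2 = 5.
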